3.0 Study Design

This is a prospective, cohort study of patients with low or moderate risk of PE (a pretest [pre-imaging] probability of PE $\leq 20\%$).

3.1 Number of Study Subjects

We will identify and enroll 2 groups of patients:

- 1) 100 patients undergoing CTPA with an estimated risk of CIN $<10\%$ (AKIrisk Score <2).
- 2) 600 patients with an AKIrisk Score ≥ 2 , randomized to CTPA (exposure to iodinated contrast media) or VQ imaging (unexposed control).

3.2 Number of Study Sites

The study will be conducted at 5 emergency care sites: IUH Methodist Hospital (also provides emergency care services for IUH University Hospital), Eskenazi Health Hospital, IUH Ball Memorial Hospital, University of Utah, and Intermountain Healthcare.

3.3 Duration of Subject Participation

Patient involvement will last one year, inclusive of follow-up review of their medical records. The primary outcome of AKI consistent with CIN will be measured once between 2 and 7 days (≥ 48 hours and ≤ 168 hours) after enrollment PE imaging. Safety outcomes will be followed for occurrences up to 7 days after the enrollment PE imaging study. Secondary study outcomes will be assessed starting at 30-days and 1-year.

4. Study Population

4.1 Subject Recruitment and Enrollment Strategy

The study is open to both genders, all races and ethnicities. This study will enroll women and minority patients. We expect approximately 60% women and 35-50% minority representation, and 1-3% of Hispanic/Latino origin. The Targeted/Planned Enrollment table was completed based on the PI's and co-investigator's ([name]) experience enrolling patients diagnosed with PE and in consideration of the preliminary data at the enrollment sites. We expect the proposed study enrollment demographics to mirror those of prior studies. Asians, Native Hawaiian or other Pacific Islanders are included at a <1% rate Targeted/Planned Enrollment Table because of their low prevalence in the local population, which mirrors National epidemiological studies of PE and a large sample of patients tested for PE from 12 emergency departments in the United States.^{101,104} Patients who are incarcerated or institutionalized are not able to participate in the research activities including an initial interview, a follow-up blood draw and interviews, will be excluded. Patients who, for other reasons cannot provide written, informed consent, a next of kin or persons with power of attorney will consent on their behalf. This study will not enroll children or pregnant women. Physiologic differences unique to neonates, children, pregnant women (and fetuses) may have some important but unknown effects on the development of CIN. This study is not designed to measure these differences and we do not expect to enroll enough of these patients to specifically investigate these differences. Furthermore, while the overall risk of exposure to ionizing radiation is equivalent between CTPA and VQ, CTPA involves linear radiation applied across the thorax and upper abdomen, whereas with VQ, the nuclear isotope is administered parenterally. As a result, fetal exposure to ionizing radiation may be higher with VQ.

Patients will be enrolled in the emergency departments of five hospitals: 1. IUH Methodist Hospital (which also provides emergency care services at IUH University Hospital), 2. Eskenazi Health (formerly Wishard) Hospital, IUH Ball Memorial Hospital, University of Utah, and Intermountain Healthcare. Patients may also complete their imaging studies and, for patients hospitalized >48 hours, may complete their initial follow-up at IUH University Hospital. Examination of data for all emergency department patients who have had a CTPA scan ordered from the two enrollment sites over the past three years reveals mean age 49 ± 16 years with 54% African American, 44% Caucasian, 0.8% Asian, 1% American Indian 1% report Hispanic Ethnicity, and 51% are females; payers include Medicare (22%), Medicaid (25%), Private or commercial insurance (19%) and self-pay (34%). The patients have a high burden of comorbidities, and approximately 65% of all patients are admitted to the hospital. These demographic data match up well with those published in the last three National Hospital Ambulatory Medical Care Surveys (NHAMCS)—a survey designed to collect data on the utilization and provision of ambulatory care services in hospital emergency and outpatient departments. Findings are based on a national sample of visits to the emergency departments and outpatient departments of non-institutional general and short-stay hospitals.⁹⁸⁻¹⁰⁰ Additionally, the table below shows the demographic characteristics of a large sample of patients evaluated for possible PE in 12 emergency departments, not including any hospitals in Indianapolis.¹⁰¹ The almost 2:1 predominance of women undergoing CTPA scanning from the emergency department setting has been shown repeatedly in the United States, and to a lesser extent, in Europe.^{55,102}

Demographics of Patients Evaluated for Pulmonary Embolism in the Emergency Care Setting

12 Centers Not Including Indianapolis

Indianapolis

	n = 7940		n = 200
	n	% or Mean	% or Mean
Age		49±16	49±16
Female	5328	67%	65%
White	4541	57%	61%
Black	2704	34%	29%
Hispanic	482	6%	9%
Asian	74	1%	1%
Other Race	139	2%	<1%

Patients will be identified under IRB approved waiver of authorization of release of medical records for the purpose of research. Both sites have comprehensive patient flow and computer order entry systems with real-time order alert systems that will be used to identify patients (IUH Methodist and IUH University Hospitals: Cerner©, Kansas City, MO; Eskenazi Health Hospital: Epic Systems Corporation©, Verona, WI). Notably, the applicant's research team is facile with alert systems within the EMR. As demonstration of the current success of the patient-identification process, over 2,275 of patients undergoing imaging studies for PE have been screened for an active research trial of nitric oxide to treat PE (www.clinicaltrials.gov, protocol NCT01939301, conducted by [name], a co-investigator on this proposal). The PI will leverage these existing alerts to identify potential study participants for the proposed study.

Following the first 3 months of enrollment, we plan to evaluate our enrollment process with administrative imaging logs (DORIS, Indiana University Health Department of Radiology) to evaluate potential bias in the enrollment protocol. Written, informed consent will be obtained from all study participants.

As a part of the informed consent process, participants will agree to have their creatinine and a urine dipstick measured at enrollment, and for investigators to draw and use blood and urine samples for purpose of research (to measure Cystatin-C and NGAL). Participants will also provide written informed consent to use blood and urine samples for measurement of biomarkers of AKI-risk in future work. Patients will also agree to return for a follow-up interview and have their creatinine measured between 2 and 7 days after enrollment, complete a telephone follow-up interview, and give permission to obtain their medical records to complete follow-up at 24 hours, 1 week, 30 days and 1 year.

The subject's EMR will be screened for initial inclusion and exclusion criteria. A study investigator or coordinator will approach the potentially eligible patients for consent. If not already documented in the EMR, the study coordinator will complete the PE PreTest Consult Score and AKIrisk Scores and determine eligibility. This process may involve the treating provider for input on the risk score results. If not already performed within 7 days, an order for a chest radiograph will be placed in conjunction with the clinical team, the study coordinator will also perform a bedside urine dipstick to identify glycosuria $\geq 250\text{mg/dL}$ (1+ or greater) for patients who have not already had a urinalysis performed within 24 hours. If the patient is eligible, the coordinator will obtain the patient's written informed consent, collect basic data, and may collect urine and blood samples.

The research associate or investigator will make every attempt to talk to the patient without distractions in or around the room. Where appropriate, the investigator will personally speak to family members in quiet family rooms. Informed consent forms will be signed at the point of care by the patient. The patient will be given adequate time to make a decision. The patient will be given a copy of the informed consent document.

4.2 Inclusion Criteria

1. Age ≥ 18 years
2. CTPA ordered by the treating provider to evaluate PE.
3. Pre-test probability of PE $\leq 20\%$ (defined using the PE Pretest Consult Score)
4. For randomization to CTPA or VQ imaging: Pre-imaging CIN risk $\geq 20\%$ (AKIrisk Score ≥ 2 points)

- A lower-risk subset of 100 patients (AKIrisk Score <2) will be enrolled and followed. These patients will complete the CTPA as ordered by their provider (not randomized). Data from this lower-risk subset, along with high-risk patients randomized to CTPA will be used will be used to validate the AKIrisk Score, alone and in combination with NGAL and eGFR_{CYS} (Study Aims 1 and 3).

4.3 Exclusion Criteria

- 1) History of pulmonary surgery or findings on chest-radiograph that may limit the accuracy of VQ imaging for the detection of PE including air-space disease occupying more than 50% of the lung field, significant mass, or pleural effusion of significant volume or associated with low-lobe air-space disease.
- 2) Clinical instability or other condition preventing randomization to CTPA or VQ imaging.
- 3) Pregnancy or ≤48 hours post-partum.
- 4) Subject unavailability for reasonable follow-up including biological sample collection, creatinine measurement, and interview, such as an insecure residence, planned travel or absence, personal or professional obligations, incarceration, and/or other reason preventing follow-up, identified at enrollment.
- 5) Active renal replacement therapy (hemodialysis or peritoneal dialysis) within 30-days of enrollment or previous physician-directed plans to initiate dialysis within 30-days of the index visit.
- 6) Prior renal transplant or planned within 30-days of enrollment.
- 7) Intravascular contrast administration within 14 days prior to enrollment or planned within 7 days of enrollment.

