- 4) Well Defined Study Population: Ideally, the selected contrast-enhanced and the non-contrast alternative(s) would result in the following: A) A well-defined patient population undergoing evaluation for a single, unified clinical disease with predictable risk and expected outcomes; B) The presence or absence of the disease in question would have minimal, if any, effect on AKI risk, and; C) At the completion of diagnostic testing (contrast-enhanced imaging or a non-contrast alternative), both groups would have a low and equal risk of subsequent nephrotoxic events (e.g. sepsis, surgery, etc.) or drugs exposures, including additional contrast media administration.
- 5) Common Diagnostic Study: To achieve the necessary study accrual, both the contrast-enhanced study and the non-contrast alternative must have reasonable availability and be performed commonly enough that treating physicians are familiar with the use of both imaging strategies.

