In the same prospective cohort, the PI has also tested the prognostic accuracy of two emerging biomarkers of acute-phase renal dysfunction in her CT cohort, Neutrophil Gelatinase-Associated Lipocalin (NGAL) and Cystatin-C (eGFR_{CYS}, expressed as eGFR calculated using Cystatin-C¹⁷), alone and in combination with the AKIrisk Score. (Table 2.)^{9,10}

As proof of concept, preliminary data also indicate that exposure to contrast media with CTPA in associated with an increased risk of AKI: The PI examined retrospective data for 100 randomly selected patients (50 male and 50 female) at low or moderate risk of PE, with VQ imaging for suspected PE and 100 matched controls (age, gender, Black race, and eGFR_{SCr}) with CTPA imaging between January and December of 2014.

Table 2. Comparison of the predictive accuracy for contrast-induced nephropathy (CIN) of Neutrophil Gelatinase-Associated Lipocalin (NGAL, alone and when included in the AKIrisk Score) and Cystatin-C (expressed as eGFR_{CYS}) to creatinine (expressed as eGFR_{SCr}).

Factor	Threshold	AUROC	Sensitivity	Specificity
eGFR _{SCr}	≤ 60 ml/min/m ²	0.55 (0.47 to 0.63)	13% (5 to 23%)	87% (83 to 90%)
NGAL	≥ 100 mg/dL	0.68 (0.60 to 0.75)	80% (64 to 91%)	63% (57 to 69%)
NGAL AKIrisk Score*	≥ 3 points	0.82 (0.75 to 0.89)	90% (76 to 97%)	60% (54 to 65%)
eGFR _{CYS} †	≤ 60 ml/min/m ²	0.76 (0.56 to 0.95)	65% (52 to 77%)	88% (84 to 90%)

*NGAL AKIrisk Score: NGAL ≥ 100 ng/dL 3 points, and 1 point each for age ≥ 50 years, diastolic hypertension ≥ 100 mmHg, and diabetes mellitus.

†There was no improvement in prognostic accuracy when eGFR_{CYS} was combined with the AKIrisk Score.

Dialysis dependent patients and renal transplant patients were excluded, as were patients who were exposed to intravascular contrast media, within 30 days prior to, or within 7 days following, the selected PE imaging study (VQ or CTPA). Findings are summarized in Table 3. Importantly, the rate of intermediate risk VQ was only 3% and the detection rate of acute PE by VQ was not lower than CTPA. Because physician assessment of increased risk of CIN is the primary reason that patients undergo VQ imaging rather than CTPA,⁶ it is not surprising that a larger proportion of patients in the VQ group had a AKIrisk Score ≥ 2 . Because VQ is usually reserved for patients at the upper-limit of overall risk AKI (CIN and other additional causes), we expect that the incidence of AKI in the

[figure not shown]

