We will record and keep results of clinical data, including literature-derived risk factors for CIN,^{18, 23, 28, 41, 58-81} as reported in the electronic medical record, reported by the clinical team, and from the patient themselves (follow-up interviews), using study-specific data collection template created and maintained on REDCap. REDCap (Research Electronic Data Capture, hosted by the Indiana CTSI) is a secure, web-based application designed to support data capture for research studies, providing 1) an intuitive interface for validated data entry; 2) audit trails for tracking data manipulation and export procedures; 3) automated export procedures for seamless data downloads to common statistical packages; and 4) procedures for importing data from external sources. We will request contact information (address, telephone number[s], email) which will be destroyed after initial follow-up and creatinine measurement, and, if applicable, notification of patients of CIN outcome, is complete. We will also obtain and store blood and urine samples for Cystatin-C and NGAL measurements. We will obtain and keep medical records, study case report forms (CRF).

As with all patients evaluated for PE in the emergency care setting, patients will remain in the care of emergency physicians throughout their emergency department stay, including completion of the PE imaging study, including reporting of PE imaging results and associated treatment, until hospital admission and transfer of care or discharge, as per usual care. The follow-up interview and blood-draw will occur in the emergency care or inpatient setting, using the standard patient-care facilities.

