5.1 Main Measurements

Collection of blood and urine samples may be obtained around enrollment and the initial follow-up (2-7-days). We will collect blood and urine samples, using standard collection methods.

Enrollment Data Collection: The study coordinator will collect the following data: age; sex; race and ethnicity; vital signs; current medications and treatments (including anticoagulation and/or thrombolysis treatment for VTE); comorbid conditions (acute and chronic); the type and severity of prior adverse reactions to iodinated contrast media; physiologic indicators of acute disease (EKG findings of cor pulmonale, indications of right-heart strain and other echocardiography data, cardiac biomarkers including troponin and brain natriuretic peptide [BNP], and lactate); and literature-derived risk factors for CIN.^{18,23,28,41,60-83} We will also record the type and volume of intravenous fluid administered 12 hours prior to and within 24 hours following the enrollment imaging study.

Baseline Creatinine Measurement If the study participant received a baseline creatinine measurement, documented in the EMR, within 24 hours of imaging around enrollment, this measurement will be used as the baseline measurement for our study. If not, we will measure a creatinine level from the blood sample collected at enrollment, if applicable.

Follow-up Creatinine Measurement The follow-up blood draw and creatinine measurement will be performed no sooner than 48 hours and no longer than 7 days (168 hours) following the enrollment imaging study using methodology established by the applicant.^{7,11,20,89} At the time of enrollment, regardless of plans for discharge or

hospitalization, study participants will be scheduled for a return visit to their site of enrollment. The patient will receive a reminder card with the date, time, and location of their follow-up appointment and a contact phone number for the study coordinator. If the patient remains hospitalized 48 hours or more following the enrollment imaging study, we will record the highest creatinine value measured during the specified follow-up time of 2-7 days, or if needed, complete the creatinine measurement. If the patient is hospitalized, but discharged prior to the follow-up period, follow-up will be completed as previously scheduled. A \$50 dollar stipend will be provided for patients that complete the return appointment as reimbursement for travel costs and time.

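### Contrast given for other reasons after the study scan is excluded only if planned and is not named for recording, so an as-randomised equivalence result cannot be checked against the arms' actual exposure

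*Combined protocol and SAP*

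**What the plan says.** **Entry.** Section 4.3 (and the synopsis, in near-identical terms) excludes "Intravascular contrast administration within 14 days prior to enrollment or planned within 7 days of enrollment". This covers past contrast and contrast already planned at enrolment.

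**Design condition.** Section 1.4 lists what a trial of this kind needs. Condition 4C is that, once diagnostic testing is complete, "both groups would have a low and equal risk of subsequent nephrotoxic events", and it names further contrast administration among those risks.

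**Preliminary comparison.** The retrospective matched comparison in section 1.5 removed later exposure by design: patients on dialysis or with a transplant were excluded, "as were patients who were exposed to intravascular contrast media, within 30 days prior to, or within 7 days following" the selected scan.

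**Recording.** Section 5.1 lists enrolment items and says that staff will "record the type and volume of intravenous fluid administered 12 hours prior to and within 24 hours following the enrollment imaging study". Contrast given after that study is not named. The follow-up subsection of 5.1 directs record review to outcomes, and the schedule in 5.3 has no exposure row. The nearest general item is in section 1.6: clinical data will be kept, "including literature-derived risk factors for CIN", drawn from the record, the clinical team and follow-up interviews.

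**Endpoint timing.** The follow-up creatinine is taken "no sooner than 48 hours and no longer than 7 days (168 hours) following the enrollment imaging study". For patients still in hospital at 48 hours or beyond, the highest value in the window is used.

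**Analysis.** Section 2.1 analyses every patient in the group assigned and tests equivalence with a 10-point margin by two one-sided 5% tests. No per-protocol or exposure-based analysis is described. The only exposure foreseen in the VQ arm is crossover to CTPA, put at under 5%.

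**The concern.** The trial asks whether avoiding contrast changes the rate of AKI. A VQ patient given contrast on day 2 for another indication, with AKI on day 5, is counted as AKI without contrast. If contrast does harm, that narrows the arm difference. In a superiority trial this would be conservative. Here the primary test is of equivalence, so it works in favour of what the trial would conclude.

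An entry criterion cannot catch contrast that nobody had planned, so the remaining safeguard is to measure it. The protocol makes low and equal later contrast a condition of the design, and its own preliminary comparison excluded such patients, but the trial has no step to verify the condition. The crossover allowance does not do this job: it concerns VQ patients who need CTPA because the question of embolism is unresolved, not contrast given for other reasons.

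Later exposure is plausible. Section 4.1 reports that "approximately 65% of all patients are admitted to the hospital" among emergency patients with CTPA ordered, and coronary disease scores a point toward the randomisation threshold. Neither fact gives a rate of later contrast.

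**Working it through.** **The plan's own figure.** There is none for later contrast. The size below rests on assumed shares and is shown as a range.

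**Inputs from the documents**
- Margin δ = 10 points; each one-sided test at 5%, z = 1.645 (section 2.1).
- 300 recruited per arm, 30% dropout and up to 5% screening or randomisation failures (section 2.1). Evaluable per arm: 300 × 0.70 = 210, or 300 × 0.70 × 0.95 = 199.5, about 200.

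**Assumptions**
- Share c of patients given other contrast before the endpoint creatinine: 10%, 15%, 20%.
- AKI without contrast: 8% (with n = 210) or 10% (with n = 200). The plan gives only an overall rate below 20%.
- True contrast effect E = 10 points, so the arms truly differ by exactly the margin.
- Each later dose in a VQ patient has the full effect E.
- A repeat dose in a CTPA patient adds a fraction r of E. The share c is the same in both arms.

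**Formulae**
- P_VQ = P0 + cE and P_CTPA = P0 + E + r·c·E
- Apparent difference D = E·[1 − c(1 − r)]
- SE = √[P_CTPA(1 − P_CTPA)/n + P_VQ(1 − P_VQ)/n]
- Chance of declaring equivalence ≈ Φ[(δ − D)/SE − 1.645]; the other one-sided test is almost always passed here.

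**One case in full** (n = 210, P0 = 8%, c = 10%, r = 0). P_CTPA = 18%, P_VQ = 9%, D = 9.0 points. SE = √(0.18 × 0.82/210 + 0.09 × 0.91/210) = 3.31 points. (10 − 9.0)/3.31 − 1.645 = −1.34, which gives 9.0%.

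**False equivalence, true effect 10 points**

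| Share c | D when r = 0 | n = 210, r = 0 | n = 200, r = 0 | n = 210, r = 0.5 | r = 1, either n |
|---|---|---|---|---|---|
| 0 | 10.0 | 5.0% | 5.0% | 5.0% | 5.0% |
| 10% | 9.0 | 9.0% | 8.6% | 6.8% | 5.0% |
| 15% | 8.5 | 11.6% | 10.9% | 7.8% | 5.0% |
| 20% | 8.0 | 14.7% | 13.6% | 8.8% | 5.0% |

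**Larger effect.** With 25% v 10% (15 points), n = 200 and r = 0, false equivalence is 0.1% at c = 0 and 1.5% at c = 20%.

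**No effect.** If E = 0, then D = 0 whatever the share, and there is no bias.

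**Timing.** If only half of the later doses fall early enough to act, a share of 10% behaves like 5% (6.8% false equivalence at n = 210, r = 0) and a share of 20% like 10% (9.0%).

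**Follow-on superiority test.** At 20% v 10%, n = 200 and r = 0, power falls from 80% with no later contrast to 70% at c = 10% and 59% at c = 20%.

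**The case against.** The case on the other side has five parts.

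1. *The upper figures are a worst case.* They need a true effect exactly at the margin, a full effect from every later dose in the VQ arm and none from repeat doses in the CTPA arm. This stands. With equal and additive exposure the error does not move from 5%.

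2. *Timing dilutes the effect.* Section 2.1 says that creatinine in contrast nephropathy typically peaks at 3 to 5 days, so a dose shortly before the draw can add little. This also stands and lowers the upper figures.

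3. *Likelihood.* A reader might infer from the admission figure that later contrast is common. The documents do not support that. The figure describes all emergency patients with CTPA ordered at two sites, not trial participants, and says nothing about further contrast. The trial also excludes clinical instability, and Table 1 sets aside body CT and coronary imaging partly because later contrast is hard to avoid there. Plausible is as far as one can go.

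4. *Capture.* A reader might infer that later contrast would leave no trace. That is too strong. The risk-factor item in sections 1.6 and 5.1, the scheduled record reviews and the discharge summaries in 6.2.4 could recover some of it. None of them names later contrast or asks for its timing or indication, so capture by arm is not assured.

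5. *As-randomised analysis suits a comparison of imaging strategies.* Agreed, and it should remain primary. It does not remove the need to know how far exposure differed before reading equivalence as evidence about contrast itself.

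**Conclusion.** The gap holds: unplanned contrast after the study scan is neither excluded nor named for recording, no exposure-based analysis stands beside the as-randomised equivalence test, and nothing checks condition 4C.

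If contrast raises AKI, the possible bias is toward equivalence. For an assumed 10–20% share, 200–210 evaluable per arm and a true 10-point effect, false equivalence lies between 5% (equal exposure, repeat doses fully additive) and about 9–15% (repeat doses add nothing). It is about 1.5% or less for a 15-point effect, and the bias vanishes with no effect.

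A reader might go further and conclude that an equivalence finding would be invalid, or that the 32% v 6% preliminary result cannot inform the trial. Neither follows. The rate of later contrast is unknown, and the sample size and margin are stated in terms of an overall AKI rate below 20% and a 10-point difference; the protocol offers the matched data as proof of concept. What follows is narrower: as written, the trial may not be able to show which of these cases applies. The change is worth making before the data are analysed.

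**What to change.** 1. **Record.** In section 5.1, use the record reviews already scheduled at 24 hours, 48–168 hours and 7 days to capture any intravascular iodinated contrast (date, time, indication) in both arms. The period runs from the study scan to the creatinine value used for the endpoint; for inpatients this is the highest value on days 2–7.

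2. **Report.** Keep the as-randomised equivalence test as primary, and tabulate later exposure by arm.

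3. **Add one supportive equivalence analysis** against the same 10-point margin. For example, divide the as-randomised difference by the between-arm difference in the proportion exposed before the endpoint creatinine. With all CTPA patients and 10% of VQ patients exposed, an apparent 9.0 points becomes 9.0/(1.00 − 0.10) = 10.0.

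4. **State its assumptions:** repeat doses add little, and later doses act fully. Where the second fails, the ratio over-corrects, so vary the minimum time between dose and creatinine that counts as exposure.

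**Cost.** A few case report form fields from reviews already planned, and a supportive estimate that is less precise than the primary one and depends on these assumptions. Randomisation and the primary test are unchanged.
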